This study aimed to examine the extent to which working memory training improves aspects of cognition, the extent to which these effects are augmented by the participants' expectations or placebos, and whether any placebo effects are retained after participants become aware of their assigned expectations among a young adult population (ages 18-30). It was predicted that there would be a main effect of training, such that those who completed the true cognitive training intervention would improve in their cognition overall more than those who completed the control cognitive training, as well as a main effect of expectation, such that those who were given a positive expectation about their training would improve in their cognition overall more than those who received a negative expectation about their training. No interaction between training and expectations was predicted. It was also predicted that both the training and expectation effects would persist after being made aware of their expectations.

Secondary aims included exploring whether individual traits, including demographic characteristics, personality, or motivation, in young adults can predict the strength of placebo effects in cognitive training, and to determine the feasibility of this study with an older adult population (ages 60+). As these were exploratory analyses, no a priori predictions were made.

Study Design

The study design was a 2 (positive expectations vs. negative expectations) x 2 (true cognitive training intervention vs. control cognitive training intervention) between-subjects Randomized Controlled Trial (RCT). Thus, participants were assigned to one of four conditions: Positive expectations with true cognitive training, negative expectations with true cognitive training, positive expectations with control cognitive training, or negative expectations with control

cognitive training. For the older adult feasibility study, only the two true cognitive training conditions with either positive or negative expectations were used.

Recruitment Strategy

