Participants for this study were recruited in two phases. The first phase included young adults (ages 18-30), who were recruited via university campus flyer advertisements and university human participant pools at each of the three study sites, University of Wisconsin – Madison, University of California, Irvine, and University of California, Riverside. The second phase included older adults (ages 60+), who were recruited through community flyer advertisements (e.g., senior community centers) and email advertisements to previous lab participants at each site.

Inclusion Criteria:

- Self-reported normal or corrected-to-normal vision
- No known neurological impairments (this includes any neurological impairments that would negatively impact participants' ability to perform perceptual or cognitive tasks or to complete long-term cognitive training; this could include neurological damage due to stroke in various brain areas; seizure conditions that would preclude the ability to view flashing images; motor control issues that preclude the ability to respond via button presses; etc.).
- Access to the internet, a computer, and a hand-held device, such as a cell phone or tablet

Exclusion Criteria:

- Self-reported non-normal or non-corrected-to-normal vision
- Neurological impairments
- No access to the internet, a computer, or a hand-held device

Procedure

Participants were first screened via email (young adults) or phone (older adults) to ensure they met all eligibility criteria. Young adults self-reported that they met eligibility criteria, while older adults were screened using the Montreal Cognitive Assessment Short – Abbreviated Telephone Version (MoCA), Geriatric Depression Scale – Short Form (GDS), and Geriatric Anxiety Scale – 10 Item Version (GAS).

During the first set of sessions, participants provided consent via an online form and then completed a pre-test cognitive battery (see Dependent Measures) online with a researcher present via Zoom. They also filled out a set of surveys about demographic information, personality traits, and other internal dispositions that may predict the extent to which they are susceptible to placebo effects.

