After the pre-test, participants were assigned to their expectation group (positive/negative) and their training group (active/control), which was randomized prior to the start of the study. They were first given their group appropriate explicit expectation presented in a series of paragraphs and images online. Those in the positive expectation group were told that the training that would

complete has previous research supporting its use as a method to enhance cognitive abilities. Those in the negative expectation group were told that the training they would complete has previous research suggesting that it is unlikely to change cognitive abilities or may even decrease participants' scores on the tests of cognitive function. Note that depending on the participants' particular training group assignment, this may or may not have been deceptive. If they were assigned to the true cognitive training intervention, there is research showing that the to-be-utilized true training increases cognitive function. As such, those that received positive expectations received accurate information and those that receive negative expectations received inaccurate information. However, there is no research showing that the control training intervention increases cognitive function. As such, those that received negative expectations received accurate information and those that received positive expectations received inaccurate information.

The participants were then given instructions on how to complete their training task. Participants were asked to complete ten 20-minute sessions of training once per day without the presence of a researcher. The true cognitive training intervention was standard working memory (*n*-back) training task. In this task, participants were shown a series of colored circles one after another. As each circle appeared, their task was to indicate whether the color matched the one presented *n*-items back in the stream by tapping on the circle. For example, if they were performing a 3-back level, if they had seen the colors red, blue, green, and red, and then they saw the color blue, they would tap the screen. The control training intervention was a trivia/quiz task, which included general trivia questions.

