9. Raven's Advanced Progressive Matrices (RAPM) is a fluid intelligence measure in which the participant is presented with a grid of elements with one of the elements missing and is asked to identify the missing element that completes the grid pattern.
10. The UC Matrix Reasoning Task is a fluid intelligence measure, similar to RAPM, in which the participant is presented with a grid of elements with one of the elements missing and is asked to identify the missing element that completes the grid pattern.
11. The Mill-Hill Vocabulary scale is a control measure that assesses vocabulary ability.
12. The Shipley Institute of Living scale is also a control measure that assesses vocabulary ability.

Secondary measures used to determine whether individual characteristics predict placebo effects in cognitive training included demographic variables (e.g., age, gender, race/ethnicity), Big Five Inventory (BFI-10), Work and Family Orientation Scale (WOFO), Grit, Behavioral Avoidance/Inhibition scales (BIS/BAS), Theories of intelligence, Schutte Self-Report Emotional Intelligence Test, and Meta-Cognitive Skills Scale.

Statistical Analysis Plan

To examine the main hypotheses, a 2 (true cognitive training vs. control training) x 2 (positive expectation vs. negative expectation) MANCOVA will be conducted on the set of 10 dependent post-test variables, with pre-test scores as a covariate. Scores will be standardized prior to analysis. If significant, post hoc analyses will be conducted as necessary (i.e., it is unlikely that every DV will be similarly impacted by placebo effects - as such, follow-up analyses separated by DV will be performed after the main analysis). A similar analysis will be conducted on the delayed test scores (controlling for pre-test scores).

The following secondary variables will be analyzed to test for moderation of placebo effects on each DV: Big Five Inventory (BFI-10) subscale scores, Motivation (BIS/BAS) subscale scores, Grit scale score, Metacognitive scale score, Fixed/growth mindset scale score, Schutte Self-Report Emotional Intelligence Test subscale scores, Work and Family Orientation subscale scores, Demographic variables, such as age and gender.

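### Three recruiting sites but no site term in the models: the analysis is valid but gives up a little precision that one extra factor could recover

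*Combined protocol and SAP*

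**What the plan says.** Under Recruitment Strategy, young adults come from "university campus flyer advertisements and university human participant pools at each of the three study sites".

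Under Study Design, "participants were assigned to one of four conditions", so the individual is the unit of allocation. Procedure adds only that the assignment was one "which was randomized prior to the start of the study". It gives no allocation ratio and mentions neither blocking nor stratification by site.

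The Statistical Analysis Plan specifies a 2 × 2 "MANCOVA will be conducted on the set of 10 dependent post-test variables, with pre-test scores as a covariate". For the later time point: "A similar analysis will be conducted on the delayed test scores (controlling for pre-test scores". Follow-up analyses by outcome come after the main test. The moderator list covers personality, motivation and similar scales and ends with "Demographic variables, such as age and gender". Site is not a factor, covariate, random effect or moderator in any of these, and no sensitivity analysis by site is described.

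**The concern.** Three campuses can differ in student population and in the staff who run the sessions. Adjusting for pre-test deals with differences in starting level. It does not deal with differences that arise after pre-test, such as how much participants gain from repeating the battery or how faithfully they complete training on their own. Whatever part of these differs by site and is not predicted by pre-test is counted as noise in every planned comparison.

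What is at stake is the precision of the two main effects, the interaction and the delayed-test contrasts. Recruitment site should be known for each participant before allocation, although the documents do not list it as a recorded variable. Adjusting for it is routine in a multi-site trial.

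**Working it through.** **Inputs from the documents.** Three sites (Recruitment Strategy); individual allocation to four conditions (Study Design); pre-test as the only adjustment (Statistical Analysis Plan). No sample size, alpha, power, site sizes, between-site variance or pre–post correlation is stated, so there is no figure to reproduce. Everything below is illustration under stated assumptions.

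**1. Cost of leaving site out.** Let ρ be the share of residual variance, after pre-test adjustment, that lies between sites. The standard error without site, relative to that with site, is k = 1/√(1 − ρ), and the effective sample size is N(1 − ρ). If the model with site has 80% power at two-sided 0.05, power without it is Φ((1.960 + 0.842)/k − 1.960).

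| Assumed ρ | k | Effective loss of N | Power |
|---|---|---|---|
| 1% | 1.005 | 1% | 79.6% |
| 5% | 1.026 | 5% | 78.0% |
| 10% | 1.054 | 10% | 75.7% |

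**2. How large ρ might be.** Let s be the SD of site means in within-site SD units and r the within-site pre–post correlation.

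- *Same site difference at pre-test and post-test.* The pooled slope is b = (r + s²)/(1 + s²), and ρ = [s(1 − b)]² / {[s(1 − b)]² + 1 − 2br + b²}. With s = 0.2 the raw share is 0.04/1.04 = 3.8%. After pre-test adjustment it is 1.2% at r = 0.5 and 0.4% at r = 0.8. With s = 0.3 it falls from 8.3% to between 2.5% and 0.8%.
- *Site difference at post-test only.* Here ρ = s²/(s² + 1 − r²). With s = 0.1 and r = 0.5, ρ = 0.01/0.76 = 1.3%. With s = 0.2 and r = 0.8, ρ = 0.04/0.40 = 10%.

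Pre-test thus absorbs most of a stable site difference and none of one that emerges later. A range of 1–5% is a reasonable working assumption, not a bound.

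**3. Chance imbalance is the same loss.** Under allocation that ignores site, a main effect has variance of about 4(s² + w)/N, where w is the within-site residual variance. The part 4s²/N is chance site imbalance, and its share of the total is s²/(s² + w) = ρ. For s = 0.2 and N = 200 its SD is 2 × 0.2/√200 = 0.028. A simulation of 20,000 permutations over three near-equal sites gave 0.029, with mean zero. This is the loss in step 1 seen from another side, not an addition to it.

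**4. Validity.** A simulated single-outcome ANCOVA without site (two groups, N = 198, r = 0.7, equal site shifts at both times with s = 0.2, 0.4 or 0.8, allocation stratified or not, 4,000 runs each) rejected a true null in 4.6–5.4% of runs. The simulation standard error is √(0.05 × 0.95/4000) = 0.3 percentage points, so these rates are compatible with 5%.

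**5. Cost of adding site.** Three levels use 2 error degrees of freedom per outcome. With unstratified allocation and an assumed N of 200, two uninformative terms inflate the variance of a main effect by about (200 − 3)/(200 − 2 − 3) = 197/195 = 1.010. At ρ near 1% the gain is roughly cancelled. The simulation agrees: at s = 0.2 and r = 0.7 (ρ = 0.65%) the SD of the estimate was 0.1038 without site and 0.1040 with it. At s = 0.4 (ρ = 2.05%) it was 0.1051 without and 0.1039 with.

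**The case against.** The strongest case against is that this is a preference between two valid analyses. Under individual randomisation, omitting a prognostic variable from a linear model does no harm beyond imprecision, and pre-test is already in the model. Pre-test is done "online with a researcher present via Zoom" and training without a researcher, so no site laboratory is described that would create large differences, and nothing says that staff, practice gain or adherence vary by campus. All of this stands. It limits the size of the point but does not remove it, because differences arising after pre-test would still go unadjusted.

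A reader might infer more than the documents support:

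- *That the effect estimates are biased or the tests too liberal.* Neither follows. Chance site imbalance averages zero and is already reflected in the model's standard error.
- *That all between-site variation stays in the error.* Only the part that pre-test does not predict does.
- *That imbalance and lost precision are two separate harms.* They are one quantity (step 3).
- *That the standard errors are wrong because the allocation list was built by site.* A site-stratified list would indeed make a model without site slightly conservative, and it would also largely remove the imbalance. The protocol does not say that the list was stratified, so this cannot be asserted.

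**Conclusion.** The point holds as a minor improvement in efficiency. The planned post-test and delayed-test analyses are valid without site. The amount given up depends wholly on ρ, which cannot be derived from the documents. The 1–5% range is an assumption. The remote format argues for its lower end, where with around 200 participants and unstratified allocation the net gain would be close to nil. A site difference that emerged only after pre-test could push the share above 5%. No stated figure in the plan changes, and no conclusion about training or expectation effects is put in doubt.

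**What to change.** Add site as a fixed factor with three levels to the post-test MANCOVA, the delayed-test MANCOVA, the follow-up analyses by outcome and the moderator models. State in the Procedure section whether the allocation list was stratified by site, since that settles how the term is justified.

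The change needs no new data beyond each participant's recruitment site and costs 2 error degrees of freedom per outcome. Timing matters: the protocol describes conduct in the past tense while the analysis plan is in the future tense, so the documents do not show whether outcomes have been seen. If they have not, prespecify the term. If they have, keep the planned model as primary and report the site-adjusted model as a labelled sensitivity analysis.
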